### **4.2 Exclusion Criteria**

For our analytic sample from secondary Medicare claims data we will exclude:

- a. Medicare beneficiaries with a diagnosis of metastatic cancer or

- b. Medicare beneficiaries enrolled in hospice any time in the 6 months before the start of the intervention

#### **4.3 Study Enrollment Procedures**

##### Patient Subjects

We will partner with two ACOs with primary care clinic locations. Prior to random assignment, we will stratify all clinics/practices based on high versus low historic prescribing rates, with the cut-point for inclusion in the study based on the distribution of overall rates for all 3 therapeutic classes using data for 2019-2020. These clinics will be randomized 1:1 to either the intervention or control arms of the study. We will work closely with leadership in each ACO over months 1-3 of the study to recruit an appropriate clinician from each clinic in the intervention arm of the study to participate in the study. A total of 30 clinicians across the two ACOs will participate in the intervention, with 30 clinics in the control group without a clinician value champion.

We will request a waiver of informed consent and waiver of HIPAA authorization for including patient data in this study. The intervention will be embedded within the health care system at the clinic level as a training program for clinicians. No patients will be recruited into this study. Although data from human subjects are involved, no contact will ever be made with patients as this project involves the use of secondary data only. Attempting to obtain authorization or consent would not be feasible as this study will involve a study population of an estimated 5,000 patients. Consent and authorization of patients for enrollment in this study would create bias, generate prohibitive study costs rendering the study unfeasible, and produce results that would not be generalizable to other health care organizations. Furthermore, contacting 5,000 subjects for written consent would increase the only risk for patients - breach of confidentiality. We will ensure subjects' protection against risk by following the measures outlined in the section below.

##### Clinician Subjects:

Clinical leaders at the two ACOs with an understanding of the scope of the project will identify and approach clinicians at each intervention clinic to take part in the Value Champions training sessions. Clinical leadership will support VCs participation in the project in re: time needed for training and de-implementation efforts.

The clinician VCs are the de-implementation intervention. The control group (clinics) have no clinician VC embedded at the clinic. We will conduct 2 interviews with approximately 8 VCs that have completed the webinar training to measure implementation outcomes. Each VC who agrees to be interviewed will be interviewed approximately 5-7 months after webinar training is complete, and a second time approximately 10-12 months after training is complete. The implementation measures are not used to assess the VCs themselves (no personal information, or health information about the VCs will be collected). These interviews will be analyzed to provide insight into the de-implementation process at each ACO; how the de-implementation intervention was tailored and taken up in the clinical setting, for example. We will report each implementation outcome, both within each ACO and across the two ACO.

An email with an information sheet attached will be sent to the Value Champions after they are identified by clinical leaders, and before the first Webinar training. Included in this email is contact information to ask questions. At the first Webinar training session, we will start

the meeting by reminding Value Champions about the information sheet, ask if there are questions, and provide contact information to use in order to ask questions privately.

We are requesting a waiver of documentation of consent to enrolled clinician Value Champions in the study.

We will mention the interviews to the clinician champions during the monthly shared learning phone calls, and in emails reminding the group of the upcoming phone calls. We will then send an email inviting the clinician Value Champions to participate, with an information sheet explaining the interviews. The email and information sheet will note that they may opt out of the interviews. The email and information sheet will also give contact information if the clinicians have questions about the interviews.

If we have not reached recruitment goals (at least 4 clinicians at each ACO – 8 clinicians total) in one week, we will ask clinical leaders at the ACOs to remind clinicians to respond to the emails by opting in or out. If we still have not reached recruitment levels two weeks after the invitation email is sent, we will ask the clinic manager to forward the recruitment email to ask for a response.

We are seeking a Waiver of Documentation of Consent in order to conduct these interviews.

## **5 STUDY INTERVENTIONS**

### **5.1 Interventions, Administration, and Duration**

No drugs or devices will be studied. The intervention is a quality improvement strategy consisting of a clinician value champion who will engage other clinicians within their clinic in an effort to decrease the use of PIMs in PLWD. Typical methods of engagement include educational meetings, facilitating conversations about evidence of harm, providing current provider-specific data on rates of prescribing, etc.

### **5.2 Handling of Study Interventions**

No drugs, devices or dietary or nutritional supplements will be used in this study. No patient level interventions will be used either.

### **5.3 Concomitant Interventions**

N/A.

#### **5.3.1 Allowed Interventions**

N/A

#### **5.3.2 Required Interventions**

N/A

#### **5.3.3 Prohibited Interventions**

N/A

## 5.4 Adherence Assessment

There is no adherence assessment for enrolled patients, as this study uses secondary data only. Although Clinician Value Champions are not study subjects, they are key to the intervention and will take part in study activities as part of their clinical care. The study team will work closely in partnership with ACO leadership to facilitate study participation and retention of the clinician value champion from each clinic in the intervention arm of the study. In addition, each champion will be assigned a mentor from the former value champion fellows to increase the likelihood of engagement.

## 6 STUDY PROCEDURES

There are no study visits, no patient-level evaluation or schedule of such evaluations planned. We will use existing Medicare claims data from each ACO to inform selection of clinics for randomization. The primary outcome (Specific Aim #1) and one of the secondary outcomes (Specific Aim #2) will be evaluated using secondary Medicare claims data 12 months after completion of the clinician value champion training program. The secondary outcome for Aim #3 will be evaluated by analyzing interviews with approximately 8 value champions conducted following the completion of the training program.

### 6.1 Schedule of Evaluations

Assessment	Months 1-3: Selection of Clinics for Randomization	Months 18-24: Evaluation of Primary & Secondary Outcomes
Medicare Claims for each ACO	X	
Rates of Prescribing of PIMs (Specific Aim #1) from Medicare Claims		X
ED Visits or Hospitalization for a fall (Specific Aim #2) from Medicare Claims		X
Implementation Outcomes From Clinician Interviews (Specific to Aim #3)		X

## 6.2 Description of Evaluations

### 6.2.1 Screening Evaluation

Screening for eligibility will be done by review of existing Medicare claims data from each ACO as described in Section 4.1 above.

#### Consenting Procedure

##### Patient Subjects

We are seeking a Waiver of Informed Consent in order to identify and include patients in the study. Although data from human subjects are involved, no contact will ever be made with patients as this project involves the use of secondary data only. Attempting to obtain authorization or consent would not be feasible as this study will involve a study population of an estimated 5,000 patients. Consent and authorization of patients for enrollment in this study would create bias, generate prohibitive study costs rendering the study unfeasible, and produce results that would not be generalizable to other health care organizations. Furthermore, contacting 5,000 subjects for written consent would increase the only risk for patients - breach of confidentiality.

##### Clinician Subjects:

We are seeking a Waiver of Documentation of Consent in order to enroll clinician Value Champions in the study. The study PI (the initial PI at the time the study commenced), [name], will send an email prior to training webinars with an attached study information sheet. During the first webinar, VC clinicians will be reminded of the information sheet by [name]. He will provide contact information both in the email and during webinar in case VCs have questions.

We are seeking a Waiver of Documentation of Consent in order to conduct a series of 2 interviews with clinician who have completed the Value Champions webinar training series. We will mention the interviews to the group during the shared learning phone calls, and in emails reminding the group of the upcoming phone calls. We will then send an email inviting the Value Champions to participate, with an information sheet explaining the interviews. The email and information sheet will note that they may opt out of the interviews. The email and information sheet will also give contact information if the clinicians have questions about the interviews.

If we have not reached recruitment goals (at least 4 clinicians at each ACO – 8 clinicians total) in one week, we will ask clinical leaders at the ACOs to remind clinicians to respond to the emails by opting in or out. If we still have not reached recruitment levels two weeks after the invitation email is sent, we will ask the clinic manager to forward the recruitment email to ask for a response.

#### Screening

##### Patient Subjects:

Screening of eligible participants will be done by the programmer/analyst at IAC by applying study inclusion / exclusion criteria as described above in Section 4.1. This screening and selection will take place months 1-3 of the study prior to the value champion intervention. All Medicare beneficiaries at eligible ACOs will be included if they

meet eligibility criteria during the intervention year.

#### Clinician Subjects

Clinician Value Champions in the intervention clinics will be identified by ACO leadership, prior to the first webinar. The ACO leadership, in consultation with [name], will determine the suitability of specific clinical staff for study participation.

We will enroll at least four Clinical Value Champions from the two ACOs to be interviewed twice after they have completed the webinar training. Clinicians will be enrolled on a first come basis. All clinicians that have completed the webinar series will be eligible.

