#### Primary & Secondary Outcomes by Specific Aim:

Specific Aim #1: The primary outcome for this study will be medication possession rates (MPR) per quarter, for the 3 therapeutic classes of PIMs - antipsychotics, benzodiazepines, and hypoglycemics using currently available Medicare claims data from each participating ACO. These beneficiary-level measures are calculated as quotients with denominator equal to the length of the quarter and the numerators equal to the days supply for prescriptions within the class filled during the quarter, plus excess days-supply from the previous period minus excess days-supply remaining at the end. Unlike many studies using medication possession rates to exam adherence, we are interested in reducing, not increasing, the percent of days covered.

Specific Aim #2: As a secondary outcome, we will also assess the incidence of falls during the study window. Falls are difficult to monitor using claims data, but Min and colleagues have developed a method that IAC and Brandeis staff (Co-Investigator [name]) have helped test for ICD-10. We will use the most conservative definition that looks for the presence of fall 'reason for visit' code on ED, ambulatory, or inpatient visit as indicated by a clinician bill (Part B).

Specific Aim #3: The five important implementation outcomes: appropriateness, fidelity, feasibility, and penetration will be assessed by analysis of interviews conducted with a group (approximately 8) of clinician value champions who have completed the webinar training.

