#### 9.4.2 Secondary outcomes

As a secondary outcome, for Specific Aim #2, we will also assess the incidence of falls during the study window. Falls are difficult to monitor using claims data, but Min and colleagues have developed a method that IAC and Brandeis staff (Co-Investigator [name]) have helped test for ICD-10. We will use the most conservative definition that looks for the presence of fall ‘reason for visit’ code on ED, ambulatory, or inpatient visit as indicated by a clinician bill (Part B). Key covariates in all of our regression models will include age and sex, both derived from the Medicare beneficiary summary files, house at IAC.

For Specific Aim #3, the five important implementation outcomes: appropriateness, fidelity, feasibility, and penetration will be assessed by analyzing interviews with clinician value champions. The Clinician interviews will provide us with data we need to assess the implementation outcomes.

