#### **10.3.4 Protocol Deviations**

We will document number of training sessions completed by each clinician value champion. Each value champion will have an assigned mentor who will conduct a monthly check-in visit to overcome challenges if they deviate from the training program and their project to tackle overuse of inappropriate medications. Mentors will keep notes of these meetings and share them with the PI and study team monthly.

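### Fidelity and feasibility are judged only from about 8 of about 30 champions, volunteers who finished training, while planned records on every champion go unused

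*Combined protocol and SAP*

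**What the plan says.** **Source of the outcomes.** Section 3 (Primary & Secondary Outcomes by Specific Aim) states that the implementation outcomes "will be assessed by analysis of interviews conducted with a group (approximately 8) of clinician value champions who have completed the webinar training". Section 9.4.2 names no other source: "The Clinician interviews will provide us with data we need to assess the implementation outcomes". Section 9.5 specifies a deductive thematic analysis of the interview data, with no rate, threshold or success criterion. Section 4.3 adds that each outcome will be reported by ACO and across both.

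**Who is interviewed.** Section 6.2.1 (Screening, Clinician Subjects) gives the rule: "Clinicians will be enrolled on a first come basis. All clinicians that have completed the webinar series will be eligible". Section 6.2.2 (Enrollment, Clinician Subjects) instead draws interviewees from champions who participated in the training. Champions may opt out (Sections 4.3 and 6.2.1).

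**How many.** Sections 4.3 and 6.2.1 (Consenting Procedure) set a goal of "at least 4 clinicians at each ACO – 8 clinicians total". If it is missed, reminders go out through ACO leaders and then clinic managers. Section 6.2.1 (Screening) has a lower figure: "We will enroll at least four Clinical Value Champions from the two ACOs to be interviewed twice".

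**What is recorded on every champion.** Section 10.3.4 says "We will document number of training sessions completed by each clinician value champion". It also gives each champion a mentor who checks in monthly and whose notes go to the study team. These records appear under protocol deviations and are linked to no Aim 3 outcome in Section 9.4.2 or 9.5.

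**The concern.** Fidelity and feasibility describe how the intervention went across the clinics assigned to it. Here they are inferred from a minority that passes three filters: completing the training (under the Section 6.2.1 wording), agreeing to be interviewed, and replying in time. The first filter removes the champions for whom the training proved unworkable, who are the most informative about feasibility.

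This matters for two reasons. Section 9.1 describes the study as a demonstration project whose purpose includes showing feasibility and acceptability, so these outcomes are not incidental. And Section 8 allows champions to withdraw, with replacement only if feasible, while the intention-to-treat analysis in Sections 9.1 and 9.5 assigns treatment by practice, so a clinic that lost its champion still counts as intervention. If the medication possession rate (MPR) shows no difference, a delivery measure for all intervention clinics would help to interpret that result, and the analysis plan specifies none.

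**Working it through.** **Inputs from the protocol**
- Interview goal: 4 per ACO × 2 ACOs = 8, which reproduces the stated total (Sections 4.3 and 6.2.1).
- Champions: 30 stated (Section 4.3). From practice counts, (32 + 26)/2 = 29 (Section 9.2.1), or (30 + 26)/2 = 28 (Section 9.2).
- Completion rate, delivery rate, and any link between volunteering and success: not given, so assumed below and shown as ranges.

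**Step 1. Coverage**
- 8/30 = 26.7%; 8/29 = 27.6%; 8/28 = 28.6%.
- With 30 champions, 30 − 8 = 22 (73%) do not contribute.
- If only the lower figure of four were met, 4/30 = 13.3%.

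**Step 2. Effect of interviewing completers only**

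Let c be the share of champions completing training, and p1 and p0 the shares delivering the project among completers and non-completers. If interviewees represent completers, they show p1. The value across all champions is c·p1 + (1 − c)·p0. The difference is

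overstatement = (1 − c)(p1 − p0).

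With p1 = 0.9 assumed:

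| p0 (assumed) | c = 0.9 | c = 0.8 | c = 0.5 |
|---|---|---|---|
| 0.5 | 4 points | 8 points | 20 points |
| 0.2 | 7 points | 14 points | 35 points |
| 0 | 9 points | 18 points | 45 points |

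For example, (1 − 0.5)(0.9 − 0.2) = 0.35. The difference is zero if c = 1 or p1 = p0.

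**Step 3. Effect of volunteering among those eligible**

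If the true share of successes is p and a success is k times as likely to be interviewed, the interviewed share is kp/(kp + 1 − p). With p = 0.6 assumed:
- k = 1: 60%, no distortion.
- k = 2: 1.2/(1.2 + 0.4) = 75%.
- k = 4: 2.4/(2.4 + 0.4) = 86%.

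**Step 4. Precision without any bias**

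If eight interviews were read as a proportion, the exact (Clopper-Pearson) 95% interval for 8/8 favourable is 63% to 100%, and for 6/8 it is 35% to 97%. By ACO there would be about four interviewees each.

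Steps 2 to 4 are illustrations. The plan does not propose to report a delivery proportion from the interviews.

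**Step 5. What the Section 10.3.4 records would add**

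Coverage for training dose rises from about 27% to all champions. Mentor notes add engagement for all champions, and project launch or replacement as far as the notes record them. Nothing in Section 10.3.4 measures penetration.

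**The case against.** The strongest reply is that this is qualitative work. A small sample is normal, Section 4.3 states the aim as insight into how the intervention was tailored and taken up, and there is no numerical estimate to bias. That stands as to form: the harm is to how far the findings can be generalised. It does not answer the point that one group is left out by rule while records covering that group are planned and unused.

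A reader might infer more than the documents support:
- **That the outcomes will certainly be overstated.** No completion rate is given, and nothing links volunteering to success. The direction is likely, not certain.
- **That every champion who disengaged or was replaced is excluded.** The Section 6.2.1 rule concerns the webinar series only. A champion who trained and then disengaged in the project phase stays eligible, as does a replacement who completed the webinars. Section 6.2.2 would also admit those who only participated.
- **That the sample is simply the keenest.** There is a goal of four per ACO, with reminders if it is missed, so balance by ACO is already largely planned.
- **That a null trial could not separate an ineffective intervention from an undelivered one.** Session counts and mentor notes would exist. What is missing is a prespecified use of them.
- **That all-clinic penetration is already logged.** Section 10.3.4 describes no such measure.

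**Conclusion.** The point holds in limited form. The implementation outcomes rest on about 27% of champions, who are self-selected and, under Section 6.2.1, restricted to those who completed training. The resulting picture of fidelity and feasibility is likely to be favourable. Its size cannot be established from the documents: across the assumed values above, the completers-only rule gives anything from 0 to 45 points on a hypothetical delivery proportion, and selective volunteering could add to that. It is zero if all complete and volunteering is unrelated to success.

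The clearest defect is that session counts and mentor notes planned for every champion are not used for Aim 3. The two wording conflicts, on completion against participation and on the minimum number interviewed, are errors in their own right. The primary MPR comparison is not affected.

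**What to change.** 1. In Sections 9.4.2 and 9.5, prespecify a descriptive report for all intervention clinics, as fidelity and feasibility measures: training sessions completed and, as far as the mentor notes record them, project engagement, project launch and champion replacement. State that it will also help interpret the primary result.
2. Keep the interviews to explain these findings. Compare interviewed with non-interviewed champions on attendance, and state the limits of the interview sample.
3. Do not claim penetration across all clinics from these data.
4. Invite non-completers to interview where the consent procedures allow. Section 11.2 notes that the interviews were added after clinician consent and have separate consent procedures, so this is more than an analysis edit.
5. Reconcile Section 6.2.1 with Section 6.2.2 on completed against participated, and the minimum of four across both ACOs with the goal of four at each.

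**Cost.** Items 1 and 2 use data already planned and need minor abstraction of mentor notes. Item 4 needs a slightly wider invitation and a check of the consent procedures. Items 3 and 5 are wording.

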#### 6.2.2 Enrollment, Baseline, and/or Randomization

##### Enrollment

##### Patient Subjects

We are using secondary data to identify Medicare beneficiaries at eligible ACO clinics, and thus seek a waiver of informed consent. Medicare beneficiaries will be enrolled in the study when they are identified, after we receive the waiver of informed consent.

##### Clinician Subjects

We are seeking a waiver of documentation of consent to enroll clinician Value Champions at the intervention clinics. Clinician Value Champions will be considered enrolled when their questions about the study have been answered, and they take part in the webinar trainings.

We are seeking a waiver of documentation of consent to enroll clinician Value Champions for 2 interviews from among clinicians who participated in the Value Champions training. Clinician Value Champions will be considered enrolled in the interviews when they indicate their willingness to participate, their questions about the 2 interviews have been answered, and they take part in the interviews.

##### Baseline Assessments

N/A

##### Randomization

We will start our sample identification by identifying clinics at each ACO that meet eligibility criteria. Half of the eligible clinics will be randomized to an intervention group, and half to usual care group.

